8.1.1 Primary endpoints

To describe the natural history of the LGMD 2E

To define of the clinical variables that more strongly relate with the evolution of the disease

To identify any possible correlation between variables

To identify any possible correlation between variables and clinical outcomes

To identify any possible correlation between phenotype and genotype

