8.1.2 Secondary endpoints

To define the better follow up routine for LGMD 2E patients in view of possible genetic differences

To define those therapies that are able to slow the progression of the disease

To ameliorate the use of sanitary resources for the management of these chronic patients.

To gain new knowledges that could be used for the development and the management of future new therapies.

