2) Blood tests: Glucose* Proteins* Hemoglobin* White blood cells* Neutrophils *INR* RATIO* CPK* LDH* Amilase* Cistatine C* AST * ALT * ALP * GGT * Bilirubin total/direct/ indirect* Creatinine* Electrolytes (Sodium – Potassium - Clorum – Calcium total/ionized)* Urine (macroscopic view - blood (Yes/No) – anomalies)*

3) Bone status: MOC - PTH pg/mL - VIT D1,25 pmol/L-VIT D 25 nmol/L*

4)Glycemic state: Insuline - Hb1aC* Pro BNP*

Autoimmune disease

Name*

Treatment*

Therapy

1) Name - posology – data – rationale

2) Prescriptions*

3) Pain therapy*

4) Steroids*

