8.4 Data sources

Data used to collect variables will include any clinical document provided by patients or available in our hospital thank to the server of the Unit of Neurology. Only official clinical charts will be considered. Clinical outcomes will be defined as the age of loss of ambulation, the age of introduction of cardiological supporting drugs and the age of introduction of respiratory supporting devices/therapies. These ages will be directly obtained from the clinical reports (on report it is reported the age of the patient) of indirectly (according to the data of the report that describes the first introduction of the drug/devices or that firstly reports the loss of the ambulation)

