8.5 Cohort dimension

Expected cohort dimension is of 33 patients that is the number of patients followed at the Neurological Unit in the last 10 years. Statistical analysis will be based on generalized linear regression models, suitable both for continuous variables both for independent ones. Variables with a nonlinear distribution will be used only in logarithmic scale. Only data corresponding to yearly visit (at least two data in two years) will be used for the linear correlation analysis and in multivariate correlation models. Furthermore, to verify the accuracy of clinical variables in

describing the evolution of the dystrophy, variables will be coupled and compared by a bivariate analysis.

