8.7 Data analysis

Analysis will be performed using generalized linear regression models suitable both for continuous variables both for independent ones. Variables with a nonlinear distribution will be transformed in logarithmic scale before the analysis to be performed. For any analysis data will be divided according to the age of the patient at the moment of the evaluation. Data will be analyzed with linear correlation both compared to the variable age both in bivariate models and multivariate models. Results obtained will be adjusted for confounding factors not related to muscular dystrophy.

Data of included patients will be globally studied and divided in two groups homogeneous for genotype.

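### The protocol seeks therapies that slow progression by relating variables to milestone ages, without tying drug exposure to its start date; a before-the-milestone yes/no coding would make a null drug look protective

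*Protocol*

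**What the plan says.** - **Aim.** Protocol 8.1.2 lists as a secondary endpoint "To define those therapies that are able to slow the progression of the disease".
- **Comparison.** Protocol 8.1.1 lists as a primary endpoint "To identify any possible correlation between variables and clinical outcomes". Section 8.7.1 repeats the link to clinical outcomes. Neither names therapies.
- **Outcomes.** Section 8.4: "Clinical outcomes will be defined as the age of loss of ambulation, the age of introduction of cardiological supporting drugs", and the age at first respiratory support. Each is one age per patient.
- **Variables.** The therapy block of 8.3 collects "Name - posology – data – rationale", with steroids as a separate item. All chart data before the recruiting visit are eligible, so drugs begun before and after a milestone are both captured.
- **Method.** Section 8.7: "Analysis will be performed using generalized linear regression models". Linear correlation is the other method named. Data are divided by age at evaluation, and adjustment covers only confounders unrelated to the dystrophy. Section 8.5 limits the correlation and multivariate models to yearly-visit data.
- **Size.** Section 8.5: "Expected cohort dimension is of 33 patients".
- **Stated limit.** Section 8.9 says that, for want of natural-history data, the study cannot give reliable information on the impact of therapies on progression.

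**The concern.** A patient can start a drug before losing ambulation only while still walking. Someone who loses ambulation at 22 has more years in which to be prescribed it than someone who loses it at 10. If each patient is labelled treated or untreated before the milestone and that label is related to the milestone age, the drug-free years before the start are credited to the drug.

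This differs from confounding by severity. It arises even when the start of the drug is unrelated to prognosis, so adjusting for severity does not remove it. Restricting to drugs begun before the milestone does not remove it either, since that restriction produces it. Dividing visits by age does not by itself move the years before the start into the untreated group.

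At stake is the therapy aim in 8.1.2. The protocol intends its results to support follow-up guidelines (section 6) and the development and management of future therapies (8.1.2). A false benefit for steroids or a cardiac drug would be carried into both.

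**Working it through.** **The plan's own figure.** The only figure is 33 patients, a count of those followed over 10 years. The protocol gives no alpha, effect size, SD or milestone age, so there is no calculation to reproduce and every input below except n = 33 is an assumption.

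**Inputs.**
- Milestone age L: normal, limited to 6 to 40 years.
- Drug start S = 5 + exponential(rate r), independent of L, so the drug has no effect.
- Treated if S < L.

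**Formula.** The chance of being treated, given L, is p(L) = 1 − exp(−r(L − 5)). It rises with L even though the drug does nothing. The group means are E[L·p(L)]/E[p(L)] for treated and E[L·(1 − p(L))]/E[1 − p(L)] for untreated.

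In the central setting (r = 0.05), p(10) = 1 − exp(−0.25) = 0.22 and p(20) = 1 − exp(−0.75) = 0.53. The late-milestone patient is more than twice as likely to be labelled treated.

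**Only starts before the milestone count.** Numerical integration gives the means. Repeated samples of 33, about 4,000 per setting, with a two-sided 5% test of the yes/no label against L give the last column.

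| Mean, SD, r | Treated | Mean L, treated | Mean L, untreated | False gain (years) | p<0.05 |
|---|---|---|---|---|---|
| 12, 3, 3% | 19% | 13.2 | 11.9 | 1.25 | 15–17% |
| 15, 5, 5% | 39% | 17.0 | 14.4 | 2.6 | 35–36% |
| 18, 6, 10% | 69% | 19.6 | 15.4 | 4.25 | 52–53% |

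The spread in the last column is between repeat simulations. In the run where direction was tallied, every significant result pointed to benefit.

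**Starts after the milestone also count.** Same three settings, exposure taken up to recruitment:
- Recruitment age independent of the milestone (uniform 20 to 45, not before the milestone): false gain about 0 to 0.5 years, p<0.05 in 4% to 5%. In the third setting many samples have almost no untreated patients.
- Recruitment a mean of 8 years after the milestone (exponential delay): false gain 0.7 to 3.6 years, p<0.05 in 10% to 26%.

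**Sensitivity to the distribution.** Gamma milestone ages (mean/SD 12/4, 15/5, 15/8, 20/10) and start rates of 5% to 20% per year give 2.6 to 11.7 years and a falsely significant benefit in 40% to 96% of studies, against about 2.5% expected in that direction. If only half the patients are ever candidates for the drug (rate 10%), this is 2.0 to 5.2 years and 19% to 38%. If later starts count (rates 3% and 10%), it is 0.1 to 4.2 years and 3% to 9%.

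**Does the remedy work?** On the gamma null data with exposure begun before the milestone, a Cox model on the age scale with time-dependent treatment gives median hazard ratios of 0.90 to 1.06 and rejection of 3% to 7%. A person-year logistic regression with exposure updated yearly (central setting, 600 runs) gives a median log odds ratio of 0.00 and rejection of 7%, slightly above nominal. Both remove the false benefit.

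**The case against.** The strongest reply is that the protocol does not commit this error. Nowhere does it say that therapy is coded as a fixed patient feature, 8.1.1 and 8.7.1 do not mention therapies, and exposure coding is often left to an SAP, which is not shown here. That stands: a reader might infer that therapies will enter as ever/never, but the text does not say so.

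A reader might also infer that the named model class forces the bias. It does not. A person-year logistic regression is a generalized linear model and can update exposure each year, and the yearly-visit rule in 8.5 is compatible with it. But the protocol does not specify it, the outcomes in 8.4 are single ages, and the linear correlation named alongside has no place for exposure to switch on.

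A third tempting reading is that any drug will look beneficial. The documents do not support that either. A plain ever/never label drawn from all chart data would include later starts, which shrinks the bias, sometimes to nothing. Counting a drug begun after loss of ambulation as exposure for that loss is invalid, though, so this is no defence. Confounding by severity may act in either direction, by an unknown amount.

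The therapy item in 8.3 most likely already means a date, since the same word is used for hospitalizations and for onset of dysphagia. Start dates should therefore be available, and only a stop date may be new.

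Finally, 8.9 already disclaims reliable therapy conclusions. It does so for lack of natural-history data, does not name this bias, and leaves the 8.1.2 aim in place. The two sections need reconciling.

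**Conclusion.** The point holds conditionally. The protocol sets a therapy aim, defines outcomes as one age per patient, names linear correlation and generalized linear regression, and gives no rule tying exposure to its start date.

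If therapy is coded as given or not given before the milestone, a null drug gains about 1.25 to 4.25 false years and reaches p<0.05 in about 15% to 53% of studies of 33. If later starts also count, the same settings give about none to 3.6 years and 4% to 26%. All of this rests on assumed milestone ages, start rates and recruitment patterns, and on start times unrelated to severity. Wider spreads in milestone age give larger figures.

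It should be settled before analysis, because the better method is known, compatible with the named model class and cheap.

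**What to change.** - **Section 8.7:** state that any association between a therapy and a milestone is estimated only with exposure updated over time, for example a person-year logistic regression or a Cox model on the age scale, with years before the start counted as untreated. State that no ever/never correlation with a milestone age is reported.
- **Section 8.3:** make explicit that a start date and, where available, a stop date are recorded for each drug, steroids included.
- **Alternative:** withdraw the 8.1.2 therapy aim or restrict it to description, consistent with 8.9.

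**Cost.** This is more than wording, because the protocol has no time-to-milestone analysis and one model must be added. The stop date is at most one more item per drug from charts already being read. Estimates will be wider, and drugs without a known start date cannot enter. The alternative costs only wording but gives up the aim of identifying effective therapies.

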8.1.2 Secondary endpoints

To define the better follow up routine for LGMD 2E patients in view of possible genetic differences

To define those therapies that are able to slow the progression of the disease

To ameliorate the use of sanitary resources for the management of these chronic patients.

To gain new knowledges that could be used for the development and the management of future new therapies.

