Guidelines will uniform the clinical approach to this disease, both on the National and the international scenario, and will improve the use of sanitary resources. Furthermore, with a phenotype-genotype correlation study, it will be possible to recognize those patients that are more at risk to develop a more severe disease.

7. Research query and objective

The lack of data on natural history of this rare disease and the need to define guidelines for the best follow up of these patients, compelled us to set up this study. In this study any investigation performed in patients affected by LGMD 2E will be considered with the aim to recognize the progression of the disease and those variables that are more useful and precise in describing its evolution. Primary objective of the study is to obtain more and better knowledge of this rare group of LGMD, describing its natural history through the analysis of clinical charts of the more affected patients possible.

To select clinical variables that are more useful to define the evolution of the disease and to identify any possible differences in clinical presentation that might be due to differences in genotype-phenotype correlation. Secondary objective of the study is to demonstrate the real impact of cardiopulmonary impairment on the prognosis of these patients.

Thank to these knowledges, to lead to a better therapeutic approach to this disease, stimulating the development of new drugs.

8. Methods

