8.2 Setting

Patients followed by the ambulatory of neuromuscular disorders of Centro Dino Ferrari, Padiglione Monteggia of Fondazione IRCCS Ca' Granda Ospedale Maggiore Policlinico (Unit of Neurology), will be recruited during the ordinary follow up routine or will be reached out to participate to this study. Furthermore, thank to the sponsorship of Gruppo familiari beta sarcoglicanopatie (GFB), more patients that are in the network of this association will be reached out from the PI of the study and eventually included. Data will be provided by patients themselves during the visit at the room number 17 of Padiglione Monteggia of Fondazione IRCCS Ca' Granda Ospedale Maggiore Policlinico (Unit of Neurology). If the patients won't be able to move and will be interested in participating to the study a collaborator of the main researcher will reach the patients at his residence to recruit him. Main source of data will be the clinical chart of the patient and all his clinical documents assessing any operation, ascertain, visits performer through the years until this moment. Main centre will be the Fondazione IRCCS Ca' Granda Ospedale Maggiore Policlinico (Unit of Neurology). Data collection will last six months and later data will be studied.

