8.7.2 Secondary endpoints: analysis

- Identify those variables that should be kept in consideration during the follow up of these patients
- To identify the variables that better describe disease progression to start a promptly therapeutic diagnosis
- To possibly identify useless analysis and examinations in these patients

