8.9 Limitation to the study

The limitations to this study relied in the rareness of this condition and therefore in the risk to have so few data that we won't be able to reach a statistical significance. Whenever few patients will participate to the study, we won't be able to get enough data to perform trustable analysis.

Another limitation is represented by the little knowledge we have nowadays about the best clinical variables to study and about the natural history of this condition. Therefore, we will analyze variables that will eventually prove to be not reliable.

Furthermore, the lack of data about the natural history of this disease won't allow us to provide reliable information about the real impact of therapies on the disease progression.

9. Protection of included patients

This study will be performed according to Good clinical practice standards and to ethical principles derived from the Helsinki declaration and to standing law for observational studies. The observational study and the linked documentation will be presented to Ethical Committee of Fondazione IRCCS Ca' Granda Ospedale Maggiore Policlinico. The study will start only once received the required authorizations according to the Centre's procedures. The ethical committee

will also approve any change to the study protocol and recruiting modalities to involve patients in the study, according to local laws.

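### Section 8.1.2 sets a secondary endpoint of finding therapies that slow the disease, which section 8.9 says the study cannot answer reliably; the item should be descriptive and exploratory

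*Protocol*

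**What the plan says.** Protocol section 8.1.2 has four secondary endpoints. The second is "To define those therapies that are able to slow the progression of the disease".

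Section 8.9, on limitations, says that the shortage of natural history data "won't allow us to provide reliable information about the real impact of therapies on the disease progression".

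Four other sections bear on the point:

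- **Section 7** gives as its secondary objective the effect of cardiopulmonary impairment on prognosis. Therapy appears only as a hoped-for consequence of the knowledge gained: "to lead to a better therapeutic approach to this disease, stimulating the development of new drugs".
- **Section 8.7.2**, the analysis of the secondary endpoints, has three items: variables to follow, variables that describe progression, and examinations that may be unnecessary. The nearest to therapy is "To identify the variables that better describe disease progression to start a promptly therapeutic diagnosis".
- **Section 8.7** plans regression and correlation analyses by age, bivariate and multivariate models, and two genotype groups. On confounding it says: "Results obtained will be adjusted for confounding factors not related to muscular dystrophy".
- **Section 8.3** collects, under therapy, "Name - posology – data – rationale", with steroids as a separate entry.

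**The concern.** An endpoint that asks which therapies are able to slow a disease is a question about treatment effect. The same protocol says it cannot give reliable information on that question. A limitation normally qualifies how firmly an endpoint can be answered. This one says that the information the endpoint needs will not be reliable, so the endpoint and the limitation cannot both stand as written.

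What is at stake is interpretation. Section 6 describes a rare disease with little published evidence and hopes that the study will lead to follow-up guidelines that also cover therapy. Section 10 plans publication. In records where treatment followed clinical judgement, treated and untreated patients may differ in severity before treatment begins. If such a difference were reported under an endpoint worded this way, it could be read as a disease-slowing effect, and there would be little other evidence to correct that reading.

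**Working it through.** No arithmetic applies. The protocol gives no treated share, effect size, standard deviation or event count for a therapy comparison, and it states no figure that could be reproduced. The check sets the sections side by side.

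1. **Do the two statements concern the same thing?** Yes. Section 8.1.2 concerns the ability of therapies to slow progression, and section 8.9 concerns the real impact of therapies on progression. Both are current text.

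2. **Does another section reconcile them?** No.
   - Section 7 places better therapy downstream of the study and sets no therapy-effect objective.
   - Section 8.7.2 has no item that relates therapy to progression. Its nearest item is about choosing variables that describe progression.
   - Section 8.7.1 refers to correlations between variables and connections with clinical outcomes. Therapy is a collected variable, so these analyses could produce a therapy association. An association does not show that a therapy is able to slow the disease.

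3. **Could the design carry the causal wording?** Not as described.
   - Section 8.1 makes the study retrospective and observational, so nobody was allocated to a treatment.
   - Section 8.7 does handle age and genotype. Its one sentence on confounding names factors unrelated to the dystrophy and does not mention severity when treatment began. Severity is a plausible reason for starting treatment and a strong candidate determinant of later progression.
   - Section 8.4 defines three clinical outcomes: the age at loss of ambulation, at introduction of cardiological supporting drugs, and at introduction of respiratory support. Two of the three are themselves starts of treatment or support. For those therapies the exposure and the outcome overlap.

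4. **Can a descriptive item be met with what is collected?** Largely, yes. Section 8.3 lists therapy name, posology, an entry called data (read here as date) and rationale. Age at start follows from a start date if that reading is right. Duration and stop date are not listed under therapy, so duration can be given only where the charts record it.

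The reason given in section 8.9 is the lack of natural history data. The argument in step 3 from design and confounding is a separate inference from sections 8.1, 8.4 and 8.7. It points the same way but is not what 8.9 says.

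**The case against.** The strongest reply is that section 8.9 already does its job: it openly warns that conclusions on therapy will be unreliable, and it does not forbid looking. The items in 8.1.2 are also loosely worded aims. Neighbouring ones, on the use of health resources and on gaining knowledge, are not measurable endpoints either. And since 8.7.2 plans no therapy output, the risk of a false claim is smaller than the endpoint alone suggests. All of this stands as a reason to treat the point as a wording correction. It does not remove the conflict, because the causal wording in 8.1.2 remains the stated endpoint.

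Three stronger readings are tempting, and the documents do not support them:

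- **Adjustment confined to factors outside the dystrophy.** A reader might infer this from section 8.7. The sentence names such factors but does not say that only these will be used. Multivariate models are planned without a list of covariates, and the SAP, which is not shown, may supply one. What can be said is that severity at treatment start is not mentioned.
- **A final report obliged to name disease-slowing therapies.** A reader might infer this from the endpoint. Section 10 says only that a report will be written and the results published.
- **A calculable loss of precision or power.** The expected cohort of 33 in section 8.5 invites such a calculation. It would need an assumed spread, treated share and number of events, for a two-group therapy comparison that the protocol does not plan. The point does not need it.

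It may also be said that the SAP can settle the matter. A SAP can add method, but the conflict lies between two sections of the protocol and has to be resolved there.

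**Conclusion.** The point holds as a contradiction within the protocol. Section 8.1.2 promises an answer on disease-slowing therapies, section 8.9 says the information for it will not be reliable, and no other section brings the two together. A causal conclusion would not be sound on the design and adjustment described.

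Its size is a matter of wording and of what the study may conclude. The size and direction of any confounding by severity cannot be derived from the document. The primary natural-history aims are not affected. The item should be corrected, but it does not put the study as a whole in doubt.

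The conclusion rests on reading the endpoint's wording as causal, which is its plain meaning, and on treatment having been given by clinical judgement, which follows from the retrospective observational design.

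**What to change.** In section 8.1.2, replace the item with: *to describe the therapies used, with age at start and, where recorded, duration, and to explore their association with progression*.

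In section 8.7.2, add the matching item. State there, in agreement with section 8.9, that any therapy association is exploratory and supports no conclusion on effectiveness. Covariate detail, including how severity at treatment start is handled, can be left to the SAP.

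The cost is an edit to each of the two sections. No new data collection is needed if the data entry in section 8.3 means date; the protocol could confirm this in passing. The downside is that the sponsor gives up an effectiveness claim that section 8.9 already says cannot be made reliably.
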